8.3. Adverse Events, Serious Adverse Events, and Other Safety Reporting

Timely, accurate, and complete reporting and analysis of safety information, including adverse events, serious adverse events, and PQC, from clinical studies are crucial for the protection of participants, investigators, and the sponsor, and are mandated by regulatory agencies worldwide. The sponsor has established Standard Operating Procedures in conformity with regulatory requirements worldwide to ensure appropriate reporting of safety information; all clinical studies conducted by the sponsor or its affiliates will be conducted in accordance with those procedures.

Adverse events will be reported by the participant (or, when appropriate, by a caregiver, surrogate, or the participant's legally acceptable representative) for the duration of the study.

For study intervention that meets the definition of a combination product, malfunctions or deficiencies of a device constituent will be reported as PQC.

Further details on adverse events, serious adverse events, and PQC can be found in Appendix 5, Adverse Events, Serious Adverse Events, Product Quality Complaints, and Other Safety Reporting: Definitions and Procedures for Recording, Evaluating, Follow-Up, and Reporting.

8.3.1. Time Period and Frequency for Collecting Adverse Event and Serious Adverse Event Information

All Adverse Events

All adverse events and special reporting situations, whether serious or non-serious, will be reported from Day 1, starting after the first dose of esketamine nasal spray, until completion of the participant's 2-week safety follow-up visit. Prior to the first dose in this long-term extension, this information will be captured as part of Study TRD3013.

Serious Adverse Events

All serious adverse events, as well as PQC, occurring during the study must be reported to the appropriate sponsor contact person by study-site personnel within 24 hours of their knowledge of the event.

Serious adverse events, including those spontaneously reported to the investigator within 30 days after the last dose of study intervention, must be reported. The sponsor will evaluate any safety information that is spontaneously reported by an investigator beyond the time frame specified in the protocol.

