9.4.5. Safety Analyses

All safety analyses will be made on the Safety/Efficacy Population.

Adverse Events

The verbatim terms used in the eCRF by investigators to identify adverse events will be coded using the Medical Dictionary for Regulatory Activities (MedDRA). Any AE occurring at or after the initial administration of study intervention through the day of last dose plus 30 days is considered to be intervention-emergent. All reported intervention-emergent adverse events will be included in the analysis. For each adverse event, the percentage of participants who experience at least 1 occurrence of the given event will be summarized.

Intervention-emergent AEs of special interest will be summarized separately grouped in the categories as described in Section 8.3.6.

Summaries, listings, or participant narratives may be provided, as appropriate, for those participants who die, who discontinue intervention due to an adverse event, or who experience a serious adverse event.

Clinical Laboratory Tests

Only clinically relevant changes in laboratory parameters that meet the definition of an AE during the study are reported by the investigator as AEs and these will be included in the all intervention-emergent AE analyses.

Vital Signs

Descriptive statistics of pulse/heart rate, respiratory rate, and supine blood pressure (SBP and DBP) values and changes from Study TRD3013 baseline will be summarized at each scheduled time point. The percentage of participants with values beyond clinically important limits will be summarized.

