5.3. Primary Endpoint(s) Analysis

The primary analysis will be based on the Efficacy analysis set which will be same as Safety analysis set (due to design of the study) using the safety data collected during both Study 54135419TRD3013 and Study 54135419TRD4010.

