5.3.2. Estimand for treatment-emergent adverse events

Primary Trial Objective: To assess the long-term safety and tolerability of esketamine nasal spray in combination with an SSRI/SNRI in participants who have completed 32 weeks of esketamine nasal spray treatment in Study 54135419TRD3013.

Estimand Scientific Question of Interest: What is the safety and tolerability of esketamine nasal spray in combination with an SSRI/SNRI in participants who have completed 32 weeks of esketamine nasal spray treatment in Study 54135419TRD3013, based on the development of treatment-emergent adverse events (AEs)?

The estimand is defined by the following 5 components:

Study Intervention: esketamine nasal spray in combination with an SSRI/SNRI

Population: participants who have completed 32 weeks of esketamine nasal spray treatment in Study 54135419TRD3013 and received at least one dose of esketamine in Study 54135419TRD4010

Variable: development of treatment-emergent AE: from the initial administration of study intervention in Study 54135419TRD3013 through the day of last dose in Study 54135419TRD4010 plus 30 days

Summary Measure: number and incidence of subjects who develop an treatment-emergent AE per person-time at risk

Intercurrent events and their corresponding strategies:

	Name of Strategy for Addressing Intercurrent
Intercurrent Events	Events and Its Description
	While on treatment: All AEs occurring through
intervention for any reason	the day of last dose plus 30 days are included in
	analysis
Withdrawal from the study	While on treatment: Same as above

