5.3.2.1. Analysis Methods

5.3.2.1.1. Primary Analysis

The verbatim terms used in the case report form by investigators to identify AEs will be coded using the Medical Dictionary for Regulatory Activities (MedDRA). Any AE occurring at or after the initial administration of study intervention in Study 54315419TRD3013 through completion the participant's 2-week safety follow-up visit in Study 54135419TRD4010 is considered to be treatment emergent. Serious AEs reported within 30 days after the last dose of study intervention in Study 54135419TRD4010 are also regarded as treatment emergent. If the event occurs on the day of the initial administration of study intervention, and either event time or time of administration are missing, then the event will be assumed to be treatment emergent. If the event date is recorded as partial or completely missing, then the event will be considered to be treatment emergent unless it is known to be prior to the first administration of study intervention based on partial onset date or resolution date. All reported treatment-emergent AEs will be included in the analysis. For each AE, the number, proportion and incidence rate of participants who experience at least 1 occurrence of the given event will be summarized. The incidence rate is defined as the numbers of participants who experience at least 1 occurrence of the AE divided by the time at risk. Time at risk is defined as time from initial administration of study intervention in Study 54135419TRD3013 until first occurrence of AE or until last dose of study intervention plus 30 days (if participant did not experience AE). To calculate time at risk if the start date of an AE is missing completely or partially, following imputation rule will be applied:

If the onset date of an adverse event is missing day only, it will be set to:

- i) First day of the month that the AE occurred, if month/year of the onset of AE is different than the month/year of initial dosing date of Study 54135419TRD3013
- ii) The day of initial dosing in Study 54135419TRD3013, if the month/year of the onset of AE is the same as month/year of the initial dose date and month/year of the AE resolution date is different
- iii) The day of initial dosing in Study 54135419TRD3013 or day of AE resolution date, whichever is earliest, if month/year of the onset of AE and month/year of the initial dosing date of Study 54135419TRD3013 and month/year of the AE resolution date are the same.

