5.3.2.1.3. Supplementary Analysis

Several supplementary analyses will be performed where a selection of AEs will be included

- Only including AEs starting at or after the initial administration of study intervention in Study 54135419TRD3013 and before the day of first dose in Study 54135419TRD4010
- Only including AEs starting at or after the initial administration of study intervention in Study 54135419TRD4010 through the day of last dose in Study 54135419TRD4010 plus 30 days. Following outputs will be repeated:
 - o Overall summary of TEAE
 - TEAE by SOC and PT
 - o TEAE by maximum severity
 - o TEAE by maximum relationship to esketamine

- o Treatment-emergent SAE
- o TEAE of special interest
- o TEAE leading to esketamine dose interruption or change
- o TEAE stratified by AE duration (end date same as start date versus end date later than start date)
- o Summary of days with TEAE
- o Proportion of TEAEs occurring on dosing days
- o Proportion of TEAEs which occur on dosing days with same day resolution
- Only including AEs starting at or after the initial administration of study intervention in Study 54135419TRD3013 through the day on which there is a switch of SSRI/SNRI or the day of last dose in Study 54135419TRD4010 plus 30 days, whichever comes first
- Only including AEs starting at or after the initial administration of study intervention in Study 54135419TRD4010 through the day on which there is a switch of SSRI/SNRI or the day of last dose in Study 54135419TRD4010 plus 30 days, whichever comes first

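### The SAP times its primary AE rate from the first TRD3013 dose, not the first extension dose: very common events then mainly reflect the parent study, and rates of death and AE-related discontinuation are diluted

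*SAP*

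**What the plan says.** **SAP.** Section 5.3 bases the primary analysis on both studies, "using the safety data collected during both Study 54135419TRD3013 and Study 54135419TRD4010". The estimand variable in 5.3.2 covers events "from the initial administration of study intervention in Study 54135419TRD3013 through the day of last dose in Study 54135419TRD4010 plus 30 days", while its population is people who completed 32 weeks in TRD3013 and had at least one TRD4010 dose. Section 5.3.2.1.1 defines the rate: "The incidence rate is defined as the numbers of participants who experience at least 1 occurrence of the AE divided by the time at risk". The clock is set by this rule: "Time at risk is defined as time from initial administration of study intervention in Study 54135419TRD3013 until first occurrence of AE". Participants without the event are followed to last dose plus 30 days. Confidence intervals for the overall proportions and rates are specified in this section.

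**Protocol.** Section 9.4.5 calls intervention-emergent "Any AE occurring at or after the initial administration of study intervention through the day of last dose plus 30 days", without naming a study. Its summary measure is a percentage, not a rate: "the percentage of participants who experience at least 1 occurrence of the given event will be summarized". Section 8.3.1 starts AE reporting after the first dose on Day 1 and adds: "Prior to the first dose in this long-term extension, this information will be captured as part of Study TRD3013". The primary objective concerns people who have already completed 32 weeks.

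**Other windows.** SAP 5.3.2.1.3 plans a parent-only analysis and an extension-only one, described as "Only including AEs starting at or after the initial administration of study intervention in Study 54135419TRD4010 through the day of last dose in Study 54135419TRD4010", with a 30-day tail and a list of repeated outputs. It gives no time-at-risk definition. SAP 5.3.1 presents the move from intervention-emergent to treatment-emergent as terminology, and Appendix 2 lists only the dropped interim analysis as a change from the protocol.

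**The concern.** The trial is meant to describe safety after 32 weeks of treatment. A first-event rate timed from the start of the parent study answers a different question, and it can err in either direction.

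For a very common event, most participants have their first occurrence in TRD3013. They then add no extension time and no extension events to that event's rate. Protocol 2.3 says that dissociation, dizziness/vertigo and nausea/vomiting tend to become less frequent with continued dosing, so for those terms the cumulative rate would overstate the extension rate.

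For deaths and AEs leading to esketamine discontinuation, the problem is selection. Nobody could enter TRD4010 without surviving and staying on esketamine to the end of the parent study. The 32 parent weeks are therefore free of these events by construction, yet they sit in the denominator.

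**Working it through.** The documents state no AE rate, so there is no figure to reproduce. All incidences and hazards below are assumptions.

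**Inputs from the documents.** The parent period is 32 weeks (32 × 7/365.25 = 0.613 years). The extension lasts up to 104 weeks and less where the product becomes accessible locally (Protocol 4.1). The tail is 30 days (30/7 weeks). The permitted delay of up to 14 days before Day 1 is ignored.

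**1. When do parent data dominate?** Let h be a constant weekly hazard and T = 32 + extension + 30/7. The parent share of first events, and of time at risk, is (1 − exp(−32h)) / (1 − exp(−hT)). With a 104-week extension T = 140.3, and the assumed 32-week incidence gives:

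| 32-week incidence | Parent share |
|---|---|
| 90% | 90% |
| 70% | 70% |
| 50% | 52% |
| 30% | 38% |
| 5% | 25% |
| 1% | 23% |

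The share passes one half at a 32-week incidence of about 47% with a 104-week extension, 34% with 52 weeks and 11% with 32 weeks. With a 26-week extension it exceeds one half at any incidence.

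**2. How far can the cumulative rate differ from the extension rate?** Let q be the 32-week risk, λ1 = −ln(1 − q)/0.613 the parent hazard per year and λ2 the extension hazard, with 2 years of extension and no tail. Then

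pooled rate = [q + (1 − q)(1 − exp(−2λ2))] / [q/λ1 + (1 − q)(1 − exp(−2λ2))/λ2].

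For q = 90% and λ2 = 0.80, this is (0.9 + 0.1 × 0.798) / (0.9/3.76 + 0.1 × 0.798/0.80) = 0.980/0.339 = 2.89 per year.

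| q | λ1 | Pooled rate, λ2 = 0.80 | Ratio to 0.80 | Events from extension | Ratio if λ2 = 0.25 |
|---|---|---|---|---|---|
| 90% | 3.76 | 2.89 | 3.6 | 8% | 9.5 |
| 60% | 1.49 | 1.15 | 1.4 | 35% | 2.9 |
| 30% | 0.58 | 0.71 | 0.9 | 65% | 1.4 |

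The pooled rate is an average of λ1 and λ2 weighted by person-time. The two rates coincide when the hazards are equal.

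**3. Events that cannot occur in parent time.** The parent share of follow-up is 32/T:
- 104-week extension: 32/140.3 = 23%
- 52-week extension: 32/88.3 = 36%
- 26-week extension: 32/62.3 = 51%

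For rare outcomes the rate falls by about that fraction.

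**4. The supplementary analysis under the only stated clock.** If TRD4010-only events are divided by time from the first TRD3013 dose, a rare event's rate is again about 23% too low with a full extension. For a common event with λ2 = 0.80, mean extension time at risk is 0.798/0.80 = 0.998 years. The rate becomes 0.798/(0.613 + 0.998) = 0.50 per year instead of 0.80.

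**The case against.** The case for the SAP is substantial.

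- The study is descriptive, with no hypothesis or success criterion, so no decision depends on which window is called primary.
- Cumulative exposure is a recognised way to describe long-term safety. Protocol 2.2.3.4 itself reports exposure in an earlier extension study with time in previous trials included. The SAP states its window openly, and Protocol section 9 leaves specific details to the SAP.
- Protocol 9.4.5 does not name the study whose first dose starts the window. The extension-only reading comes from combining it with 8.3.1, which governs collection.
- Parent-only and extension-only analyses are both planned, so change between periods will be visible.

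Two stronger readings are tempting but not supported. A reader might infer that the headline rate is mostly a parent-study rate for all AEs. It is not: at 30% parent incidence in the second table, 65% of counted events come from the extension. A reader might also infer that anyone with a parent-study event drops out of the extension analysis. Counting is per AE, so an earlier dizziness event removes no time at risk for cystitis. Other outputs in the same SAP section, such as days with any TEAE and TEAEs on dosing days, also use later events. Nor do the documents say that all AEs lessen: Protocol 2.2.3.4 says blood pressure rises did not appreciably attenuate.

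These points narrow the concern without removing it. The supplementary analysis has no clock of its own, and the only clock in the AE analysis starts in TRD3013. Its list of repeated outputs does not name AEs leading to discontinuation; the overall summary may contain them, but the SAP does not say so. The selection effect on deaths and discontinuations is a bias in the headline rate, not a matter of labels.

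**Conclusion.** The concern holds in a limited form. The primary AE rate departs from the window that Protocol 8.3.1 and 9.4.5 imply together, and Appendix 2 does not record it. The estimand also sits awkwardly: its population is defined by completing 32 weeks, but its variable counts events within those weeks.

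For any-TEAE and very common terms, the headline rate mainly reflects the parent study. The threshold is a 32-week incidence of about 47% with a full extension and constant hazard, and lower with shorter follow-up. For uncommon events with long follow-up this is not so. For deaths and AEs leading to esketamine discontinuation, the rate is diluted by about 23% with a 104-week extension and 36% with 52 weeks; this follows from follow-up lengths and entry criteria and needs no assumed AE incidence beyond the event being rare. The planned TRD4010-only analysis reduces the problem, provided its time at risk is defined.

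The remaining magnitudes rest on assumed incidences and hazards. The change is worth making before the tables are produced.

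**What to change.** - Make the TRD4010-only window the primary AE analysis. Time at risk should run from the first TRD4010 dose to the first AE on or after that dose, otherwise to last dose plus 30 days.
- Report the overall proportions, incidence rates and 95% confidence intervals there, including AEs leading to discontinuation.
- Keep the cumulative TRD3013 plus TRD4010 analysis as supplementary.
- Align the estimand variable in SAP 5.3.2 and record the departure from the protocol's AE analysis in Appendix 2.

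First-event counting per AE can stay; the correction concerns the origin of the clock. The data are already collected and most outputs are planned, so the cost is SAP wording and table relabelling. The downside is shorter person-time and somewhat wider confidence intervals in the headline table.

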If the onset date of an adverse event is missing both day and month, it will be set to the earliest of:

- i) January 1 of the year of onset, as long as this date is after the initial dosing date of Study 54135419TRD3013.
- ii) one day after initial dosing date in Study 54135419TRD3013, if this date is the same year that the AE occurred.

A completely missing onset date of an adverse event will be set to the initial dosing date in Study 54135419TRD3013.

If the end date of an AE that is not recorded as ongoing is missing completely or partially, following imputation rule will be applied:

- For AEs with outcome Fatal, the AE end date is the death date
- The missing day of resolution of an adverse event will be set to the last day of the month of resolution.
- If the resolution date of an adverse event is missing both day and month, it will be set to the earlier of the date of withdrawal, study completion, or December 31 of the year.
- A completely missing resolution date of an adverse event that is not recorded as ongoing will be set to the date of study completion/discontinuation.

For a total number of participants with treatment-emergent AEs, SAEs,... (not on SOC, PT level), the 95% confidence interval of the proportion and incidence rate will be calculated. For proportion, the 95% Clopper-Pearson confidence interval will be calculated. The 95% confidence interval of the incidence rate will be based on a Poisson model with development of treatment-emergent AE as dependent variable, an intercept and log (time at risk) as offset.

Summary tables will be provided for treatment-emergent AEs:

- AEs
- AEs (SOC, PT level only for most common TEAE) stratified by AE duration
- End date same as start date
- End date later than start date (ongoing AEs to be classified in this group)
- Serious AEs (SAEs)
- AEs leading to discontinuation of each study agent within the study intervention
- AEs by severity
- AEs by relationship to each study agent within the study intervention
- AEs leading to dose interruption/dose modification of each study agent within the study intervention.

In addition to the summary tables, listings will be provided for participants who:

- Had SAEs
- Had AEs leading to discontinuation of study intervention.
- AEs of special interest (Appendix 7)

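### The onset-date imputation has no floor at the first TRD4010 dose, so undated AEs recorded in the extension can be dated before it began: time at risk is too short, and the SAP leaves their study period open

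*SAP*

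**What the plan says.** The imputation rules in SAP 5.3.2.1.1 are introduced for one purpose: "To calculate time at risk if the start date of an AE is missing completely or partially, following imputation rule will be applied". They then distinguish three cases.

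- **Day missing.** "First day of the month that the AE occurred, if month/year of the onset of AE is different than the month/year" of the first TRD3013 dose. Otherwise the date is tied to that dose.
- **Day and month missing.** The earliest of "January 1 of the year of onset, as long as this date is after the initial dosing date of Study 54135419TRD3013" and "one day after initial dosing date in Study 54135419TRD3013, if this date is the same year that the AE occurred".
- **Everything missing.** "A completely missing onset date of an adverse event will be set to the initial dosing date in Study 54135419TRD3013".

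The first TRD4010 dose appears in none of them, and the rules do not ask which study recorded the AE. The SAP has no other onset imputation.

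In the same section, time at risk runs from the first TRD3013 dose to the first occurrence of the AE, or to last dose plus 30 days if there is none. The confidence interval for the overall incidence rates comes from a Poisson model with log time at risk as offset.

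Protocol 8.3.1 starts AE reporting in TRD4010 after its first dose. On earlier events it says: "Prior to the first dose in this long-term extension, this information will be captured as part of Study TRD3013".

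SAP 5.3.2.1.3 splits AEs by start date. One analysis covers the parent period, up to the first TRD4010 dose. Two start at that dose: one runs to last dose plus 30 days ("Only including AEs starting at or after the initial administration of study intervention in Study 54135419TRD4010 through the day of last dose"), and the other stops earlier if the SSRI/SNRI is switched. Missing start dates are not mentioned there.

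**The concern.** The rules would suit a single study, where the first dose is the earliest possible treatment-emergent onset. Here two studies are joined. For an AE first recorded in TRD4010, protocol 8.3.1 supplies a much later earliest date, TRD4010 Day 1, and the rules do not use it.

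Two things are at stake. The first is certain under the rules as written: time at risk in the primary incidence rate ends too early for such an AE. The second is conditional. If the imputed date also decides the period in 5.3.2.1.3, AEs recorded after 32 weeks of treatment move out of the extension tables, although safety after those 32 weeks is the primary objective.

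**Working it through.** The plan gives no figure to reproduce, so the check applies the rules literally and compares each imputed date with TRD4010 Day 1.

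**Gap between the two first doses.** Day 1 is the TRD3013 Week 32 visit or up to 14 days later (SAP 5.1.1). Nominally 32 × 7 = 224 days, and 224 + 14 = 238 days. These are nominal because the parent study's visit windows are not in the documents.

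**When the imputed date precedes Day 1.**

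- Completely missing: always, by the whole gap.
- Day and month missing: when onset is in the calendar year of Day 1. The rule gives the day after the first TRD3013 dose if that falls in the same year, otherwise 1 January, which precedes Day 1 unless Day 1 is itself 1 January.
- Day missing: when onset is in the calendar month of Day 1, unless Day 1 is the 1st.
- Partial dates in later months or years, respectively, stay after Day 1.

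**Example.** First TRD3013 dose 10 March 2021; Day 1 = that date + 224 days = 20 October 2021.

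| True onset | Day missing | Day and month missing | All missing |
|---|---|---|---|
| 28 Oct 2021 | 1 Oct 2021 (before Day 1) | 11 Mar 2021 (before) | 10 Mar 2021 (before) |
| 5 Dec 2021 | 1 Dec 2021 (after) | 11 Mar 2021 (before) | 10 Mar 2021 (before) |
| 15 Jun 2022 | 1 Jun 2022 (after) | 1 Jan 2022 (after) | 10 Mar 2021 (before) |

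**Share of extension-onset AEs dated before Day 1.** This was simulated with 100,000 draws per cell. The assumptions are not from the documents: first TRD3013 dose uniform over one calendar year, Day 1 224 to 238 days later, and true onset uniform from Day 1 to the end of follow-up plus 30 days.

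| What is missing | 26 weeks | 52 weeks | 104 weeks | Days before Day 1 |
|---|---|---|---|---|
| Everything | 100% | 100% | 100% | 224 to 238 |
| Day and month | 71% | 46% | 24% | 1 to 237 |
| Day only | 6.8% | 3.8% | 2.0% | 1 to 30 |

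The last row can be checked by hand. About half of a 30-day month, 15 days, is left after Day 1, and the onset range is 7 × weeks + 31 days: 15/213 = 7.0%, 15/395 = 3.8%, 15/759 = 2.0%.

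**Time at risk.** Take an AE that truly began 200 days after Day 1 with onset completely missing. True time at risk is 224 + 200 = 424 days; the rule gives 0. The log of zero is undefined, so the offset fails unless a day is added. Measured from Day 1, the imputed onset is at −224 days.

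**With a floor at Day 1.** No imputed date precedes Day 1 in any cell above. In the 200-day example, time at risk becomes 224 days.

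**The case against.** The strongest reply is that the onset rules are there only to compute time at risk. Inclusion with missing dates has its own rule in SAP 5.3.2.1.1, which keeps an event as treatment-emergent unless it is known to precede first dosing. If that rule carries over to the windows in 5.3.2.1.3, undated AEs stay in the extension analyses. This stands: a reader might infer that extension AEs are moved into the parent period and lost, but the SAP does not say that imputed dates drive the selection. It does not say the opposite either, and the time-at-risk problem is within the rule's own stated purpose. The same applies to AE duration and days with AE. A reader might infer that both are inflated, but nothing states that imputed onsets feed them.

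Four further points limit the concern.

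- Protocol Appendix 5 (10.5.1) says collection starts at consent, which may come up to 4 weeks before Day 1. On that reading, an AE recorded in TRD4010 could truly precede Day 1 and the floor would misplace it. The conflict with 8.3.1 is real, but 28 days cannot account for a shift of 224 or more.
- The primary estimand starts at the first TRD3013 dose, so AE counts and proportions in the combined analysis are untouched. The error in the rate is upward, which is conservative for safety.
- SAEs, AEs leading to discontinuation, AEs of special interest and deaths are listed individually, so none of these would vanish from the report.
- Visits are weekly or two-weekly and eCRF discrepancies are queried, so completely missing onsets may be few. The documents give no count.

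**Conclusion.** The concern holds, for a limited set of AEs. For AEs recorded in TRD4010, the stated rules give onset dates that protocol 8.3.1 rules out. This applies to every completely missing onset, and to partial dates only in the Day 1 month (day missing) or Day 1 year (day and month missing). The certain consequence is understated time at risk, down to zero, and so an overstated primary incidence rate when that AE is taken as the participant's first relevant event. The conditional consequence is that, if the same date splits the periods in 5.3.2.1.3, such AEs leave both extension-start analyses and enter the parent-period one.

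The documents do not support the view that most AEs with only a day missing are affected. The proportion is 29/30 = 97% only among AEs in the month of Day 1, with first doses spread evenly over a 30-day month. Across the extension it is about 2% to 7% under the assumptions above.

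The conclusion rests on protocol 8.3.1 governing when AE collection starts and on the nominal 32-week interval. The overall effect cannot be sized, because the number of AEs with missing onset is unknown, and it may be small.

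**What to change.** In SAP 5.3.2.1.1, add that for AEs first recorded in TRD4010 the imputed onset is the later of the rule's date and the first TRD4010 dose date, but not after the AE end date. Keep the TRD3013 floor for AEs recorded in TRD3013.

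In SAP 5.3.2.1.3, state that AEs with missing onset are assigned to periods by this date, which is equivalent to assigning them by the study that collected them.

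Reconcile protocol 8.3.1 with Appendix 5 (10.5.1) on when AE collection starts, since the floor depends on it. State also whether a day is added to time at risk, because a completely missing onset recorded in TRD3013 would still give zero.

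The cost is one or two SAP sentences and a small programming change. No new data are needed.
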